#### **9.6. Pharmacokinetic/Pharmacodynamic Analysis**

PK/pharmacodynamic assessments will be summarized using descriptive statistics. Correlation analyses will be performed to assess associations between ONT-534 PK parameters and safety, and antitumor activity, including tumor size and best response. PK/ pharmacodynamic assessments and analyses will be handled separately and outside of the study SAP.

#### **9.7. Baseline Descriptive Statistics**

Baseline and demographic characteristics will be summarized. Additional details on disease characteristics will be presented in the study SAP.

#### **9.8. Tabulation of Individual Subject Data**

All data collected will be presented by subject data listings.

## **10. SUPPORTING DOCUMENTATION AND OPERATIONAL CONSIDERATIONS**

### **10.1. Regulatory, Ethical, and Oversight Considerations**

#### **10.1.1. Institutional Review Board/Ethics Committee Process**

The study will be performed in accordance with ethical principles that have their origin in the Declaration of Helsinki and are consistent with ICH/GCP, and applicable regulatory requirements.

In obtaining and documenting informed consent during the Screening period, the Investigator must comply with applicable local regulatory requirements (e.g., 45 CFR Part 46, 21 CFR Part 50, 21 CFR Part 56) and should adhere to ICH GCP. Prior to the beginning of the study, the Investigator should have the IRB/EC's written approval for the protocol and the written ICF(s) and any other written information to be provided to the study subjects.

The Investigator must obtain IRB/EC approval for the investigation. Initial IRB/EC approval, and all materials approved by the IRB/EC for this study, including the subject signed ICF and recruitment materials, must be maintained by the Investigator and made available for inspection.

##### **10.1.1.1. Written Informed Consent**

The subject's signed and dated ICF must be obtained before conducting any study procedures and prior to starting intervention or administering study intervention. See Section 8.1.1.1.

##### **10.1.2. Study Discontinuation and Closure**

This study may be temporarily suspended or prematurely terminated if there is sufficient reasonable cause as described in Sections 7.3 and 7.4. Written notification, documenting the reason for study suspension or termination, will be provided by the Sponsor to the Investigator at each investigational site and the Regulatory Authority in each country where this study is being conducted. If the study is prematurely terminated or suspended, the Investigator will promptly inform study subjects, the IRB/EC, and the Sponsor will provide the reason(s) for the termination or suspension. Study subjects will be contacted, as applicable, and be informed of changes to the study visit schedule.

If suspended, the study may resume once concerns about safety, protocol compliance, and data quality are addressed, and satisfy the Sponsor, IRB/EC and/or Regulatory Authorities (e.g., FDA, Medicines and Healthcare Products Regulatory Agency [MHRA]).

##### **10.1.3. Confidentiality and Privacy**

Subject confidentiality and privacy are strictly held in trust by the participating Investigators, their staff, and the Sponsor and their interventions. This confidentiality is extended to cover testing of biological samples and genetic tests in addition to the clinical information relating to subjects. Therefore, the study protocol, documentation, data, and all other information generated will be held in strict confidence. No information concerning the study, or the data, will be released to any unauthorized third party without prior written approval of the Sponsor.

All research activities will be conducted in as private a setting as possible.

The study monitor, other authorized representatives of the Sponsor, representatives of the IRB/EC, or the regulatory agencies may inspect all documents and records required to be maintained by the Investigator, including but not limited to, medical records (office, clinic, or hospital) and pharmacy records for the subjects in this study. The clinical study site will permit access to such records.

The study subject's contact information will be securely stored at each clinical site for internal use during the study. At the end of the study, all records will continue to be kept in a secure location for as long a period as dictated by the reviewing IRB/EC, institutional policies, or Sponsor requirements.

Study subject research data, which is for purposes of statistical analysis and scientific reporting, will be transmitted to and stored in a secure clinical study database. This will not include the subject contact or identifying information. Rather, individual subjects and their research data will be identified by a unique study identification number. At the end of the study, the study databases will be de-identified and archived at a secure location.

#### **10.1.4. Safety Oversight and Safety Review Committee**

Safety oversight will be the responsibility of the SRC, which is a multidisciplinary committee with the objectives to evaluate safety data, provide input and recommendations on study conduct and risk mitigation related to the following concerns:

- Are there any newly identified or potential risks with study treatment?
- Has the benefit/risk profile of ONCT-534 changed?
- Should the study be amended, paused, or stopped?
- In collaboration with Investigators, should dose escalation proceed to the next dose level?
- What is the appropriate RP2D?

The SRC is composed of cross-functional representatives including the Sponsor and the Phase 1 Study Investigators. The SRC will convene as needed to review cumulative data and to make recommendations for study conduct. The SRC will review the safety data, and any PK, pharmacodynamics, and efficacy data from each dose cohort in Phase 1 and will make the decision to move to the next dose level based upon their review of the data. Based on the totality of safety, PK and clinical data, the SRC may recommend dose level(s) between or above the initial dose levels, or alternate dosing schedule(s). The SRC will also propose the 2 dose levels or schedules to be evaluated in the Phase 2 expansion portion based upon available safety, PK, pharmacodynamics, and efficacy data. The SRC activities for this study are described in the SRC Charter.

#### **10.1.5. Study Monitoring**

Clinical study monitoring is conducted to ensure that the rights and well-being of study subjects are protected, that the reported study data are accurate, complete, and verifiable, and that the

conduct of the study is in compliance with the currently approved protocol/amendment(s), with ICH GCP, and with applicable regulatory requirement(s).

The Sponsor or designee will conduct site visits at the investigation facilities or virtually for the purpose of monitoring any aspect of the study. The Investigator agrees to allow the monitor to inspect the drug storage area, study drug stocks, drug accountability records, subject charts, and study source documents, and other records related to study conduct. When on-site monitoring is not possible (e.g., during a global pandemic), and where regulatory, local, and institution policies allow, remote study monitoring may be performed.

The Investigator(s)/institution(s) will permit study-related monitoring, audits, IRB/EC review, and regulatory inspection(s) by providing direct access to source data/documents to the Sponsor or their designees.

Before an investigational site can enter a subject into the study, a study monitor, on behalf of the Sponsor, will provide the Investigator and the study team training on the protocol, study drug, data collection, study procedures, safety processes, and the clinical monitoring plan.

During the study, a monitor from the Sponsor or representative will have regular contacts with the investigational site, for the following:

- Provide information and support to the Investigators.
- Confirm that facilities remain acceptable.
- Confirm that the investigational team is adhering to the protocol, that data are being accurately recorded in the eCRFs, and that study drug accountability checks are being performed.
- Perform source data verification. This includes a comparison of the data in the eCRFs with the subject's medical records at the hospital or practice, and other records relevant to the study. This will require direct access to all original records for each subject (e.g., clinic charts).
- Record and report any protocol deviations not previously sent to the Sponsor or designee.
- Confirm AEs and SAEs have been properly documented in the eCRFs.
- Confirm all SAEs have been forwarded to the Sponsor and those SAEs that meet criteria for reporting have been forwarded to the IRB.

The monitor will be available between visits if the Investigator(s) or other staff needs information or advice.

#### **10.1.6. Quality Assurance and Quality Control**

Each clinical site will perform internal quality management of study conduct, data and biological specimen collection, documentation, and completion. An individualized quality management plan will be developed to describe a site's quality management.

Following written standard operating procedures, the monitors will verify that the clinical study is conducted; and data are generated; and biological specimens are collected, documented

(recorded), and reported in compliance with the protocol, ICH GCP, and applicable regulatory requirements (e.g., GLP, Good Manufacturing Practices).

The investigational site will provide direct access to all study-related documents, source data/documents, and reports for the purpose of monitoring and auditing by the Sponsor or designees, and inspection by local and Regulatory Authorities.

Authorized representatives of the Sponsor, a Regulatory Authority, an EC, or an IRB may visit the site to perform audits or inspections, including source data verification. The purpose of a Sponsor audit or inspection is to systematically and independently examine all study-related activities and documents to determine whether these activities were conducted, and data were recorded, analyzed, and accurately reported according to the protocol, GCP guidelines of the ICH, and any applicable regulatory requirements. The Investigator should contact the Sponsor immediately if contacted by a regulatory agency about an inspection.

The final study protocol, including the final version of the ICF, must be approved, or given a favorable opinion in writing, by an IRB or EC as appropriate. The Investigator must submit written approval to the Sponsor before he or she can enroll any subject into the study.

The Investigator is responsible for informing the IRB or EC of any amendment to the protocol in accordance with local requirements. In addition, approval of all advertising used to recruit subjects for the study are to follow the rules of the IRB/EC and other Regulatory Authorities, if appropriate. Protocol amendment approval by the IRB/EC is required, and annually, if appropriate.

The Investigator is also responsible for providing the IRB with reports of any reportable serious adverse drug reactions from any other study conducted with the study drug. The Sponsor will provide this information to the Investigator.

Progress reports and notifications of serious adverse drug reactions will be provided to the IRB or EC according to local regulations and guidelines.

### **10.1.7. Data Handling and Record Keeping**

#### **10.1.7.1. Data Collection and Management Responsibilities**

Data collection is the responsibility of the clinical study staff at the site under the supervision of the site Investigator. The Investigator is responsible for ensuring the accuracy, completeness, legibility, and timeliness of the data reported.

All source documents should be completed in a neat, legible manner to ensure accurate interpretation of data.

Data recorded in the eCRF derived from source documents should be consistent with the data recorded on the source documents.

Clinical data (including AEs, concomitant medications, and expected adverse reactions data) and clinical laboratory data will be entered into a 21 CFR Part 11-compliant electronic data capture system provided by the Sponsor or designee. The data system includes password protection and internal quality checks, such as automatic range checks, to identify data that appear inconsistent, incomplete, or inaccurate. Clinical data will be entered directly from the source documents.

#### **10.1.7.2. Study Records Retention**

Study documents should be retained for a minimum of 2 years after the last approval of a marketing application in an ICH region and until there are no pending or contemplated marketing applications in an ICH region or until at least 2 years have elapsed since the formal discontinuation of clinical development of the study intervention. These documents should be retained for a longer period, however, if required by local regulations. No records will be destroyed without the written consent of the Sponsor, if applicable. It is the responsibility of the Sponsor to inform the Investigator when these documents no longer need to be retained.

#### **10.1.8. Protocol Deviations**

A protocol deviation is any noncompliance with the clinical study protocol, ICH or GCP. The noncompliance may be either on the part of the subject, the Investigator, or the study site staff. As a result of deviations, corrective actions are to be developed by the site and implemented promptly.

All deviations must be addressed in study source documents and reported to the Sponsor or designee as per agreed communication channels. Protocol deviations should be sent to the reviewing IRB/EC according to their policies. The site Investigator is responsible for knowing and adhering to the reviewing IRB/EC requirements.

### **10.2. Financial Disclosure**

Investigators will provide the Sponsor with sufficient, accurate financial information in accordance with local regulations to allow the Sponsor to submit complete and accurate financial certification or disclosure statements to the appropriate Health Authorities.

Investigators are responsible for providing information on financial interests during the course of the study and for 1 year after completion of the study.

### **10.3. Publication Policy**

All information concerning ONCT-534, including but not limited to this protocol, Sponsor operations, patent applications, formulas, manufacturing processes, scientific data, and formulation information, supplied to the Investigator by a Sponsor representative and not previously published, is considered confidential and remains the sole property of the Sponsor. The Investigator must agree to use this information solely for the purposes of carrying out this study and must not use it for other purposes without the Sponsor's advanced written consent.

The information developed in this study will be used by the Sponsor in connection with the continued development of ONCT-534 and thus, may be disclosed to other clinical Investigators or government regulatory agencies. The Investigator is obligated to provide the Sponsor with all data obtained in the study.

Results of this study will be disclosed or published for the study as a whole as either interim or final results at the discretion of the Sponsor in consultation with the Investigators. No Investigator or group of Investigators may disclose or publish results without the Sponsor's written permission.

## APPENDIX 1. SUPPORTIVE INFORMATION

**Table 6: Eastern Cooperative Oncology Group Performance Status**

Grade	Description
0	Fully active, able to carry on all pre-disease performance without restriction.
1	Restricted in physically strenuous activity but ambulatory and able to carry out work of a light or sedentary nature, e.g., light house work, office work.
2	Ambulatory and capable of all self-care but unable to carry out any work activities. Up and about more than 50% of waking hours.
3	Capable of only limited self-care, confined to bed or chair more than 50% of waking hours.
4	Completely disabled. Cannot carry on any self-care. Totally confined to bed or chair.
5	Dead.

**Table 7: Karnofsky Performance Status**

Score	Status
100	Normal with no complaints; no evidence of disease.
90	Able to carry on normal activity; minor signs or symptoms of disease.
80	Normal activity with effort; some signs and symptoms of disease.
70	Cares for self; unable to carry on normal activity or do active work.
60	Requires occasional assistance, but able to care for most of his personal needs.
50	Requires considerable assistance and frequent medical care.
40	Disabled; requires special care and assistance.
30	Severely disabled; hospital admission is indicated although death is not imminent.
20	Very sick; hospital admission necessary; active supportive treatment necessary.
10	Moribund; fatal processes progressing rapidly.
0	Dead.

**Table 8: Cockcroft-Gault Formula for Estimated Glomerular Filtration Rate**

$\text{Male CL}_{\text{cr}} \text{ (mL/min)} = \frac{(140 - \text{age}) \times \text{Body Weight (kg)}}{72 \times \text{Serum Creatinine (mg/dL)}}$
---

**Table 9: New York Heart Association Classification of Severity of Heart Failure**

Class	Patient Symptoms
Class I	No symptoms with normal physical activity. Normal functional status.
Class II	Mild symptoms with normal physical activity. Comfortable at rest. Slight limitation of functional status.
Class III	Moderate symptoms with less than normal physical activity. Comfortable only at rest. Marked limitation of functional status.
Class IV	Severe symptoms with features of heart failure with minimal physical activity and even at rest. Severe limitation of functional status.

**Table 10: Hy's Law**

1	ALT or AST $\geq$ 3 times ULN
2	Total bilirubin > 2 times ULN, without elevated serum alkaline phosphatase
3	No alternate explanation, such as viral hepatitis A, B, or C; pre-existing or acute liver disease; or another drug capable of causing the observed injury

## APPENDIX 2. RECIST 1.1 AND PCWG3 RESPONSE CRITERIA

Disease responses will be evaluated according to RECIST guidelines (Version 1.1) (Eisenhauer et al., 2009) ([RECIST 1.1 – RECIST \(eortc.org\)](#)) and PCWG3 criteria (Scher et al., 2016).

A short summary is given below.

### RECIST 1.1 Criteria for Assessment of Extra-skeletal Disease

#### Measurable Disease:

Tumor lesions: measurable lesions are defined as those that can be accurately measured in at least one dimension (longest diameter (LD) to be recorded) with the following:

- A minimum size of 10 mm by CT scan (CT scan slice thickness no greater than 5 mm).
- A minimum size of 10 mm caliper measurement by clinical exam (lesions that cannot be accurately measured with calipers should be recorded as nonmeasurable).
- A minimum size of 20 mm by chest X-ray.

All tumor measurements must be recorded in millimeters (or decimal fractions of centimeters).

Malignant lymph nodes: To be considered pathologically enlarged and measurable, a lymph node must be  $\geq 15$  mm in short axis when assessed by CT scan. At baseline and in follow-up, only the short axis will be measured and followed.

#### Nonmeasurable Disease:

All other lesions (or sites of disease), including small lesions ( $LD < 10$  mm or pathological lymph nodes with  $\geq 10$  to  $< 15$  mm short axis), as well as truly nonmeasurable lesions, are considered nonmeasurable disease. Lesions considered truly nonmeasurable include leptomeningeal disease, ascites, pleural/pericardial effusions, inflammatory breast disease, lymphangitic involvement of skin and lung, and abdominal masses/abdominal organomegaly identified by physical exam that is not measurable by reproducible imaging techniques.

#### Bone Lesions

For the purposes of this study, bone metastatic lesions should be recorded at baseline and followed during treatment using PCWG3 criteria (see below). Bone lesions should not be recorded as target or nontarget lesions to be followed by RECIST Version 1.1 criteria; this includes bone lesions with a soft tissue component and soft tissue lesions extending from a bone lesion.

#### Lesions with Prior Local Treatment

Tumor lesions situated in a previously irradiated area or in an area subjected to other locoregional therapy are not considered measurable unless there has been demonstrated progression in the lesion.

#### Target Lesions

All measurable lesions up to a maximum of 5 lesions per organ, representative of all involved organs, should be identified as target lesions and recorded and measured at baseline. A maximum of 10 target lesions total should be selected on the basis of their size (lesions with the LD) and their suitability for accurate repeated measurements (either by imaging techniques or clinically). A sum of the LD for all target lesions will be calculated and reported as the baseline sum LD. The baseline sum LD will be used as reference by which to characterize the objective tumor response.

Prostate and prostatic bed lesions should NOT be selected as target lesions, according to PCWG3 criteria.

#### Nontarget Lesions

RECIST Version 1.1 criteria require unequivocal quantification of the changes in tumor size for adequate interpretation of the sum of target lesions. Consequently, when the boundaries of the lesion are difficult to delineate, the lesion should not be considered a target lesion.

#### Guidelines for Evaluation of Measurable Disease

Use of CT, MRI, or PET scans is discussed in Section 8.2. Ultrasound, endoscopy, and laparoscopy should not be used to measure tumor lesions. Cytology and histology can be used to differentiate between PR and CR in rare cases (e.g., after treatment to differentiate between residual benign lesions and residual malignant lesions).

The same method of assessment and the same technique should be used to characterize each identified and reported lesion at baseline and during follow-up. Imaging-based evaluation is preferred to evaluation by clinical examination when both methods have been used to assess the antitumor effect of a treatment.

**Table 11: Evaluation of Target Lesions**

Complete Response	Disappearance of all target lesions. Any pathological lymph nodes (whether target or nontarget) must have reduction in short axis to < 10 mm.
Partial Response	At least a 30% decrease in the sum of the LD of target lesions, taking as reference the baseline sum LD.
Stable Disease	Neither sufficient shrinkage to qualify for PR nor sufficient increase to qualify for PD, taking as reference the smallest sum LD since the treatment started.
Progressive Disease	At least a 20% increase in the sum of the LD of target lesions, taking as reference the smallest sum on study (this includes the baseline sum if that is the smallest on study). In addition to the relative increase of 20%, the sum must also demonstrate an absolute increase of at least 5 mm. The appearance of one or more new extra-skeletal lesions is also considered progression. For bone lesions, refer to PCWG3 criteria for determining progressive disease.

**Table 12: Evaluation of Nontarget Lesions**

Complete Response	Disappearance of all nontarget lesions.
Stable Disease or Incomplete Response	Persistence of one or more nontarget lesion(s).

Progressive Disease	Appearance of one or more new extra-skeletal lesions and/or unequivocal progression of existing nontarget lesions. For bone lesions, refer to PCWG3 criteria for determining progressive disease.
---------------------	---

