### 9.5.4. Analysis of the Antitumor Endpoints

Evaluation of prostate cancer response to treatment (RECIST v1.1 and PCWG3) is described in [Appendix 2](#).

The objective response rate (ORR) is defined as the proportion of efficacy-evaluable subjects with a response to treatment (defined as CR or PR). The number, percentage, and exact 95% CI will be presented.

The CR Rate is defined as the proportion of efficacy-evaluable subjects with a CR to treatment. The number, percentage, and exact 95% CI will be presented.

The duration of response (DOR) is defined as the time (in months) between initial response (CR or PR) and the date of first disease progression, relapse, or death for efficacy-evaluable subjects.

DOR will be analyzed using Kaplan-Meier methods. Further details on censoring rules will be described in the SAP.

The progression-free survival (PFS) is defined as the time (in months) between first study treatment dose date and the date of first disease progression or death from any cause. PFS will be analyzed using Kaplan-Meier methods. Further details on censoring rules will be described in the SAP.

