**Table 13: Evaluation of Best Overall Response: Subjects with Target (+/- Nontarget) Disease**

Target Lesions	Nontarget Lesions	New Lesions a	Overall Response
CR	CR	No	CR
CR	Non-CR/non-PD	No	PR
CR	Not evaluated	No	PR
PR	Non-PD or not evaluated	No	PR
SD	Non-PD or not evaluated	No	SD
Not Evaluated	Non-PD	No	NE
PD	Any	Yes or No	PD
Any	PD	Yes or No	PD
Any	Any	Yes	PD

a A New bone metastatic lesions should not be considered as a 'Yes' response; only new extra-skeletal lesions.

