**Table 14: Evaluation of Best Overall Response: Subjects with Nontarget Disease Only**

Nontarget Lesions	New Lesions	Overall Response
CR	No	CR
Non-CR-non-PD	No	Non-CR/non-PD a
Not all evaluated	No	NE
Unequivocal PD	Yes or No	PD
Any	Yes	PD

a 'Non-CR/non-PD' is preferred over 'stable disease' for nontarget disease since SD is increasingly used as endpoint for assessment of efficacy in some studies so to assign this category when no lesions can be measured is not advised.

Subjects with global deterioration of health status requiring discontinuation of treatment without objective evidence of disease progression at that time should be classified as having symptomatic deterioration. Every effort should be made to document the objective progression, even after discontinuation of treatment.

In some circumstances, it may be difficult to distinguish residual disease from normal tissue. When evaluation of CR depends on this determination, it is recommended that the residual lesion be investigated (fine needle aspiration/biopsy) prior to confirming the CR status.

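### Tables 11 and 12 set different complete-response standards for nontarget lymph nodes, so a subject whose nodes normalise can be scored below CR

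*Combined protocol and SAP*

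**What the plan says.** All the response tables are in Appendix 2.

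- **Nonmeasurable Disease** includes "pathological lymph nodes with $\geq 10$ to $< 15$ mm short axis". Target lesions are chosen from measurable lesions, so nodes of this size can only be followed as nontarget disease.
- **Table 11 (target lesions), CR row:** "Any pathological lymph nodes (whether target or nontarget) must have reduction in short axis to < 10 mm".
- **Table 12 (nontarget lesions), CR row:** "Disappearance of all nontarget lesions". The next row, stable disease or incomplete response, is "Persistence of one or more nontarget lesion(s)". Neither row mentions node size.
- **Table 13 (target disease, with or without nontarget)** has the row "CR Non-CR/non-PD No PR": target CR, nontarget neither CR nor progression, no new lesions, overall PR.
- **Table 14 (nontarget disease only)** has the row "Non-CR-non-PD No Non-CR/non-PD". This outcome is neither CR nor PR.

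Section 9.5.4 counts CR or PR towards ORR and adds: "The CR Rate is defined as the proportion of efficacy-evaluable subjects with a CR to treatment". Both rates use the efficacy-evaluable population. The Synopsis (Section 1.1) lists ORR, CR rate and DOR under the Phase 2 primary objectives.

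**The concern.** Table 12 supplies the nontarget entry for Tables 13 and 14. A node that shrinks from 12 mm to 7 mm is normal by the Table 11 threshold, but it has not disappeared. Two assessors looking at the same scan can therefore reach different overall responses, depending on which table they follow.

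At stake are three descriptive measures under a primary objective that also includes comparing two doses. Cohorts have up to 16 evaluable subjects, so one or two discordant readings are visible in the reported rates. Section 4.1 describes a multi-center study, and Section 8.2 describes no central reading of response scans that would make scoring uniform.

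**Working it through.** The plan states no figure on this point, so there is none to reproduce. The check is to trace two subjects through the tables under both readings. For each, assume no new lesions and a response confirmed at least 4 weeks later.

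**Subject A.** A non-nodal target lesion disappears, and a nontarget node shrinks from 12 mm to 7 mm short axis.

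| Step | Table 12 read literally | Table 11 node rule applied |
|---|---|---|
| Target lesions (Table 11) | CR | CR |
| Nontarget (Table 12) | node still present: incomplete response | node < 10 mm: CR |
| Overall (Table 13) | PR | CR |

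PR and CR both count towards ORR. Of the endpoints in Section 9.5.4, only the CR rate changes.

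**Subject B.** Bone disease plus nontarget nodes of 10 to < 15 mm, with no target lesion. All nodes shrink to 6 mm.

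| Step | Table 12 read literally | Table 11 node rule applied |
|---|---|---|
| Nontarget (Table 12) | incomplete response | CR |
| Overall (Table 14) | Non-CR/non-PD | CR |

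Here the subject moves between non-responder and responder. CR rate and ORR both change. So does DOR, because a subject never scored CR or PR contributes no response duration.

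**Can Subject B be enrolled and counted?** Yes.

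- Inclusion criterion 6 (Section 5.1) admits evaluable bony disease without a measurable lesion.
- Appendix 2 (Bone Lesions) bars bone lesions from being target or nontarget, so small nodes can be the only disease followed by RECIST.
- Sections 9.2 and 9.5.4 do not restrict the ORR denominator to measurable disease.

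**Size of one reclassification.** With 16 evaluable subjects per cohort (Section 4.1.2), one subject is 1/16 = 6.25 percentage points. As an illustration with assumed counts and exact (Clopper-Pearson) 95% intervals:

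- 0/16 = 0%, interval 0 to 20.6%
- 1/16 = 6.25%, interval 0.2 to 30.2%

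**Formal decision.** Sections 9.1.2 and 9.5.2 define response for the Simon design as a PSA reduction of at least 50%. Tables 11 to 14 do not enter it.

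**The case against.** The strongest reply is that the rule is already in the plan. Table 11 names nontarget nodes explicitly. Its sentence is phrased as a requirement, but a 10 mm threshold would do no work for nontarget nodes if they had to vanish as well. The nonmeasurable-disease paragraph names no node below 10 mm as pathological, so a 7 mm node can properly be regarded as no longer a persisting lesion. Appendix 2 also defers to the RECIST 1.1 guideline and says of itself: "A short summary is given below".

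Much of this stands. A reader might infer from Table 12 that subjects with normalised nodes will be scored below CR. The documents do not support that, because an assessor who reads the tables together can reach CR. The risk is inconsistent scoring.

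It does not remove the problem. Section 8.2 calls the criteria a modified RECIST 1.1 and sends the reader to Appendix 2 for the details, so a site cannot tell whether the missing clause in Table 12 is a modification or an omission. For Subject B there is no target lesion, and so no reason to consult a table titled for target lesions.

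Three further inferences are tempting and fail:

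- **That Table 11 has the same gap for target nodes.** Its second sentence is the node rule, and it makes sense only if nodes below 10 mm qualify.
- **That a subject with only nontarget nodes can never be an objective responder.** Table 14 gives CR when nontarget disease is CR, so he responds if the nodes vanish, even on the literal reading. The absence of a PR category in Table 14 is a separate matter.
- **That the CR rate is biased by a calculable amount.** If a share q of complete responders had nontarget nodes that normalised without vanishing, and every assessor ignored Table 11, the reported rate would be the intended rate times (1 − q). For an assumed 10% rate and q from 30% to 60%, that is 10% × 0.7 = 7% down to 10% × 0.4 = 4%. The documents give neither input, so this is not an estimate.

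**Conclusion.** The two tables conflict on nontarget nodes, and the literal reading of Table 12 gives a result at odds with the Table 11 threshold. The consequence is limited. With target lesions in CR, the CR rate can lose a subject and ORR does not move. With nontarget disease only, CR rate, ORR and DOR can all be affected. The size is 6.25 percentage points per affected subject in a full cohort of 16. The number affected is unknown, because the documents do not say how many subjects will have nontarget nodes or how often such nodes normalise without disappearing. CR rate and ORR are reported with exact intervals and no test of either is specified; the PSA-based Simon decision is unaffected. It is worth correcting because the measures sit under a primary objective and the correction is simple.

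**What to change.** Change the CR row of Table 12 to: *Disappearance of all non-nodal nontarget lesions, and all nontarget lymph nodes < 10 mm short axis.* In the row below it, state that a node < 10 mm short axis does not count as persistence. Carry the same rule into the SAP's response derivation. No change to Table 11 is needed.

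The cost is a wording change in one appendix table and its counterpart in the SAP. It needs no new data, scans or visits, and leaves the sample size unchanged.
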